8.1.2 Agent Ordering and Agent Accountability

The investigator, or a responsible party designated by the investigator, must maintain a careful record of the inventory and disposition of all agents received using the NCI Drug Accountability Record Form (DARF).

9 BIOMARKER, CORRELATIVE, AND SPECIAL STUDIES

9.1 Correlative Studies

9.1.1 Required: Assessment for MEK activation in pre-trial tumor material

10 unstained slides of formalin fixed paraffin embedded tumor tissue will be collected from all patients who have pre-trial tumor material available. No biopsy will be performed for the purpose of this correlative study. This tumor tissue will be used to assess phopho-ERK (Western blot or ELISA), Ki-67 markers, blood vessel density, and MAPK activation markers (by whole-exome and RNA sequencing). With participant consent, tissue will be stored for future research.

Samples will be delivered to the [name] Lab at Cincinnati Children's Hospital Medical Center.

[name] Laboratory T7

[name] [name]

[contact]

9.1.2 NF-QOL studies

NF-QOL will be mandatory for all patients eligible to complete the questionnaire. See Appendix G. For patients under the age of 16 years of age, the patient will complete the NFTI-QOL in

collaboration with the parent proxy. Patients 16 and older will complete the questionnaire independently.

9.1.3 Special Studies - Neuroimaging Studies

Patients will have MRI brain and spine with and without contrast performed prior to initiation of therapy, after courses 3, 6, 9, 12, 16, 20, 26 until progression or end of therapy. MRI spine should be performed at the same time when obtaining MRI Brain when clinically indicated.

Stratum 1 patients: Volumetric measurements of VS: Traditionally, VSs have been measured using either 1-dimensional measurements (in the long axis) or 2-dimensional measurements (calculated by taking the square root of the product of the short axis-long axis measured to the plane perpendicular to the face of the temporal bone). However, the irregular shape of VSs, as determined by the unique anatomy of the IAC and cerebellopontine angle, makes it difficult for linear measurements to accurately and fully represent growth for the entire tumor. As a result, VS growth may be underestimated by linear measurement criteria. Semi-automated volumetric analysis overcomes these limitations since it uses data from 3 dimensions. The coefficient of variation (COV) ranges from 0.6% to 6.8% and is generally below 5% for lesions greater than 1 cc. 12 Volumetric analysis not only better reflects tumor size, but also allows accurate detection of smaller changes in tumor size compared to standard solid tumor response criteria (e.g., RECIST criteria). This ability to detect small changes in size is critical for tumors with slow growth rates such as VS, and, when used in clinical trials, helps limit exposure to potentially toxic and/or inactive agents. Trials for NF- related tumors, such as plexiform neurofibromas, are now routinely using volumetric changes as the primary endpoint, typically choosing a 20% increase for progression and 20% decrease for radiographic response. 45

10 STUDY CALENDAR

	Pre- therapy	Courses 1-12 ^H	Courses 13-26 ^H	Completion/ Discontinuation Of Treatment
PHYSICAL ASSESSMENTS				Ì
Medical history	X	X ^A	X	X
Physical exam /height/weight	X	X ^A	X	X
Vital signs	X	X ^A	X	X
Performance status	X	X^{A}	X	X
Neurologic exam	X	X ^A	X	X
Smoking Status	X			
Hearing evaluation (stratum 1)#	X	X ^C	X^{C}	
LABORATORY EVALUATIONS				
CBC - WBC, HgB, Hct, Platelets, ANC, ALC B	X	X ^A	X^{A}	X
PT and INR for those patients on warfain		X	X	
Serum Chemistry - Sodium, Potassium, Bicarbonate, Chloride, Calcium, BUN, Creatinine, Glucose, Phosphorous, Magnesium, Albumin, Total Protein ^B	X	X ^A	X^{A}	X
SGPT (ALT), SGOT(AST), Alkaline phosphatase, Total Bilirubin ^B	X	X ^A	X^{A}	X
CPK **	X	X ^A	X^{A}	
Serum or urine pregnancy test (for females of childbearing potential)	X	X ^A	X ^A	
Echocardiogram (ECHO)	X	X ^C	X^{C}	
12-lead EKG	X			
Ophthalmology evaluation	x D	x ^D	x ^D	X
Pulse Oximetry	X			
Chest X Ray	\mathbf{X}^{E}			
Growth plate assessment	X	X ^C	X ^C	
IMAGING ASSESSMENTS				
Brain MRI	X	X ^C	X ^C	X
Spine MRI	X	X ^{C, F}	$X^{C, F}$	X F
CORRELATIVE STUDIES				
NF1-QOL	X	Every 3 courses	Every 4 courses	
Pre-trial tumor materials (if available)	X			

	Pre- therapy	Courses 1-12 ^H	Courses 13-26 ^H	Completion/ Discontinuation Of Treatment
--	-----------------	------------------------------	-------------------------------	--

- A. To be done prior to each course. See Section 5.3. Height does not need to be recorded for patients >18 years of age after initial measurement. Childbearing potential are those female patients who have reached menarche.
 - # Audiology will include measurement of pure tone thresholds and determination of word recognition scores
- B. To be done more frequently throughout the duration of treatment if required to monitor toxicities.
- C. To be done prior to initiation of therapy, after courses 3, 6, 9, 12, 16, 20, 26 until progression or end of therapy. The assessment is a tibial x-ray (AP and lateral views) of the right knee. If abnormalities are detected on routine X-rays, MRI scan of both knees should be performed. Growth plate assessments should be done for patients under the age of 18 only, unless growth plate closure is documented.
- D. Baseline and following any visual disturbance during treatment. See section 5.2
- E. To be done if pulse oximetry is < 95% or if clinically indicated during treatment. See section 5.2
- F. MRI Spine should be done at the same time points as the standard MRI brain, if clinically indicated.
- G. Formalin fixed paraffin embedded tumor tissue will be collected from all patients who have pre-trial tumor material available
- H. All evaluations to be completed within 7 days of anticipated start date of the next course.

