1.2 Secondary Objectives

- 1.2.1 To determine the radiographic response rate of VS (defined as an decrease in VS volume by $\geq 20\%$ compared to baseline) during selumetinib treatment
- 1.2.2 To describe MRI characteristics of the tumors before and after treatment
- 1.2.3 To evaluate the feasibility of collecting pre-trial tumor samples in NF2 patients
- 1.2.4 To determine if pre-trial tumor samples indicate activation of the MAPK pathway:
- 1.2.5 To evaluate the effect of selumetinib on quality of life using the NFTI-QOL scale for patients ≥ 16 years of age

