2.2.2 Safety Data

AZD6244 Hydrogen-Sulfate Capsule

Safety data from a phase 1 study of the Hyd-Sulfate capsule formulation are available at dose levels of 25 mg BID (n=6), 50 mg BID (n=7), 75 mg BID (n=7), and 100 mg BID (n=8). One DLT was reported in the first 22 days of dosing in the 75 mg BID cohort (CTCAE grade 3 fatigue that resolved with discontinuation of drug). Two DLTs (pleural effusion and rash, both CTCAE grade 3) were reported in the first 22 days of dosing in the 100 mg BID cohort. The MTD of selumetinib Hyd-Sulfate capsule was determined to be 75 mg BID.

The most frequently reported adverse events were fatigue, dermatitis acneiform, nausea, diarrhea, and peripheral edema. All AEs of dermatitis and fatigue for patients treated in the 75 mg BID cohort were considered treatment-related. The majority of AEs were CTCAE grade 1 or 2 in intensity. However, 33/56 of patients experienced at least one CTCAE grade 3 event during the study, of which 18/56 experienced at least one treatment-related AE > Grade 3. The majority of grade 3 events were reported by only one patient. Events that were reported in more than one patient include left ventricular dysfunction, nausea, vomiting, fatigue, febrile infection, lower respiratory tract infection, increased blood alkaline phosphate, GGT increased, hypoxia, dermatitis acneiform, and hypertension. Fatigue was the most commonly reported CTCAE grade 3 or higher AE. The only grade 4 event in the study was a single episode of hypoglycemia.

Eighteen patients had permanent discontinuation of study treatment due to at least one adverse event. Five patients had AEs of fatigue reported as contributing to discontinuation of treatment. Two patients each had AEs of anorexia, vomiting, nausea and LV dysfunction, also reported as being at least partly contributing to discontinuation of study treatment. Seven patients had at least one SAE that was considered treatment-related, with hypertension being the only SAE reported more than once.³⁰

LVEF

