5.5 Duration of Therapy

In the absence of treatment delays due to adverse event(s) or disease progression, treatment may continue for 26 courses (approximately two years) or until one of the Off Treatment Criteria found

in Section 5.6 applies.

During the second year of treatment, procedures consistent with good clinical care will continue. Patients will be seen monthly for medical history, physical exam (including height, weight, vital signs, and performance status), neurologic exam, dates of drug administration, relevant laboratory evaluations and routine neuro-imaging assessments. Therapy-related events will be recorded per standard assessments, including adverse events, date of disease progression, date of last follow up, date patient goes off treatment and date off study. Please review the table in Section 10 of the protocol for the required assessments and intervals. All patients must discontinue treatment with selumetinib following the completion of 26 courses of treatment.

5.6 **Duration of Follow Up**

Discontinuation of Treatment

At the discontinuation of treatment, the "Off Treatment Date" is to be recorded in the CRF and is to be consistent with the reason given for going off treatment. The "Last Treatment Date" is defined as the last date that the patient received protocol based therapy. Date of "off treatment" must be the greatest of the date of last treatment, date of procedure, date of patient assessment, notification of patient/family decision, or decision made by the physician that resulted in the patient being taken off protocol treatment. The reason for discontinuation of treatment must be documented by the attending investigator in the medical record and recorded in the CRF. The "Off Treatment Date" and the "Last Treatment Date" should be the same for patients that complete all protocol defined treatment.

Patients will be considered Off Treatment for the following reasons:

- 5.6.1 Development of unacceptable toxicity as outlined in Section 5.2.1 that does not resolve within 14 days.
- 5.6.2 Non-compliance with study guidelines
- 5.6.3 Progressive disease, as outlined in section 11.1 and 11.2
- 5.6.4 Development of a medical or psychiatric illness, that in the investigator's judgment renders the patient incapable of further therapy on this protocol
- 5.6.5 The patient, parent or legal guardian refuses further treatment on this protocol
- 5.6.6 Pregnancy
- 5.6.7 Completion of maximum number of courses of treatment with selumetinib

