
Patients will be monitored every 6 months for 2 years after protocol treatment. Ongoing AE's should be monitored as per section 7.4.3. Additionally, patients will be followed for initiation of subsequent therapy for NF2, selumetinib related adverse events (including cardiac toxicities), date of disease progression, date of last follow up, and date of death.

Patients who are off protocol therapy must be followed until an Off Study Criterion is met. Ongoing AE's should be monitored as per section 7.4.3.

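### No quality-of-life score is scheduled when a patient stops selumetinib, so objective 1.2.5 would rest on scores taken while patients remain on treatment

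*Combined protocol and SAP*

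**What the plan says.** Section 1.2 sets the objective: "To evaluate the effect of selumetinib on quality of life using the NFTI-QOL scale", for patients aged 16 and over. Section 9.1.2 states that "NF-QOL will be mandatory for all patients eligible to complete the questionnaire", but names no time points, so the Section 10 calendar governs. Its questionnaire row is labelled NF1-QOL, which I take to be the NFTI-QOL of Appendix G. The row has a mark before therapy, then "Every 3 courses" for courses 1-12, "Every 4 courses" for courses 13-26, and nothing in the last column, for completion or discontinuation.

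That last column is marked for history, physical examination, vital signs, performance status, neurologic examination, blood count, chemistry, liver tests, ophthalmology and MRI.

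Section 5.6 lists the reasons for leaving treatment. They include "Development of unacceptable toxicity as outlined in Section 5.2.1 that does not resolve within 14 days", progression, non-compliance and refusal. Section 6.2.1 adds the need to reduce below dose level -1. After treatment, "Patients will be monitored every 6 months for 2 years after protocol treatment", and "patients will be followed for initiation of subsequent therapy for NF2, selumetinib related adverse events" along with progression and survival dates. Quality of life is not on that list. Section 13 contains no quality-of-life analysis and no rule for missing scores.

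**The concern.** The objective asks what the drug does to quality of life, but after baseline the plan measures it only in patients still taking the drug on an assessment date. Stopping for toxicity, refusal or clinical deterioration is plausibly related to how the patient feels, so the missing scores are unlikely to be a random subset. A score that was never collected cannot be recovered in analysis. The trial is single-arm, so no control group loses scores in the same way. A summary of the scheduled scores could then show stable or improved quality of life partly because patients who were doing worse had left.

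**Working it through.** **1. Plan figures available.** The documents give no number for quality of life, so there is none to reproduce. The only design figure needed is the stratum size in Section 13.2: 9 + 8 = 17, or 34 if both strata complete stage 2. The stated properties of that design reproduce: early stopping 0.95^9 = 0.630 (stated 0.63) and 0.75^9 = 0.075 (stated 0.075), and exact power 0.812 (stated 0.81). They concern the primary endpoints and are untouched by this point.

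**2. Schedules side by side.** One course is 28 days, or 4 weeks.
- Questionnaire: baseline, then courses 3, 6, 9, 12, and (counting on from 12) 16, 20, 24. The calendar gives intervals, so these course numbers are inferred.
- MRI and stratum 1 hearing (footnote C): baseline, then after courses 3, 6, 9, 12, 16, 20, 26.

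The two agree at six on-treatment visits and differ only at the last.

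**3. Age of the last score at stopping.**
- Before the end of course 3 (3 × 4 = 12 weeks): no post-baseline score.
- From then to course 12: less than 3 courses, so up to almost 12 weeks.
- Courses 13-26: less than 4 courses, so up to almost 4 × 4 = 16 weeks.
- A patient who completes 26 courses: 26 - 24 = 2 courses, or 8 weeks.

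**4. Which stops are missed.** Progression found at a scheduled MRI or hearing test through course 20 usually falls at a visit that also has a questionnaire. The stops that escape are mainly those between assessments: toxicity, refusal, and progression declared on clinical grounds.

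**5. How many patients.** No discontinuation rate is given for this trial. Let f be the share stopping off-schedule, taken as an assumption:

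| f | of 17 | of 34 |
|---|---|---|
| 0.10 | 1.7 | 3.4 |
| 0.20 | 3.4 | 6.8 |
| 0.30 | 5.1 | 10.2 |
| 0.40 | 6.8 | 13.6 |

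These are upper limits for objective 1.2.5: enrolment starts at age 3, the objective starts at 16, and 17 is reached only if stage 2 opens.

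**6. Effect on the mean.** If a share f drops out of the average altogether, the observed mean change differs from the full mean by f × (mean change in those who stay - mean change in those who stop). With f from 0.10 to 0.40, the error is one tenth to two fifths of that difference. The documents give no value for the difference, so no figure in scale points can be derived. Patients who stop later keep their earlier scores, which reduces the error.

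**The case against.** Much of the case on the other side stands. A baseline score exists, and late stoppers contribute every earlier score. Progression found on schedule is largely covered, as shown above. The eight NFTI-QOL items (balance, hearing, facial weakness, sight, mobility, role and outlook, pain, mood) do not ask about fatigue, rash or diarrhea, so stopping for those reasons need not move the score much. Some toxicity that interrupts dosing may cause no symptoms. The direction of any bias is therefore plausible but not established. Quality of life is the last of five secondary objectives, with no hypothesis or test attached.

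The empty cell could be an extraction fault. However, neighbouring rows keep their marks in that column, and the follow-up text in Section 5.6 omits the questionnaire too.

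A reader might infer a size from Section 2.2.2: "Eighteen patients had permanent discontinuation of study treatment due to at least one adverse event". Dividing by the 56 in the paragraph before gives 18/56 = 32%, or 5.5 of 17. The documents do not support carrying that over. The sentence has no denominator of its own, and the dose cohorts listed there total 6 + 7 + 7 + 8 = 28. That study also used flat doses up to 100 mg twice daily, whereas this trial doses by body surface area with a 50 mg single-dose cap. In the pediatric phase 1 study at 25 mg/m², 3 of 24 patients had dose-limiting toxicity (12.5%), but such events are not discontinuations. Neither figure is a rate for this trial.

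**Conclusion.** The gap is real: no score is scheduled at stopping, and no other section supplies one. Following the plan as written loses scores that are plausibly related to outcome. The last score is absent for stops before the end of course 3, and otherwise up to almost 12 weeks old in courses 1-12 or 16 weeks in courses 13-26. Under an assumed 10-40% stopping off-schedule, about 2-7 of at most 17 patients per stratum are affected, fewer at ages 16 and over.

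Two stronger readings go too far. One is that the plan certainly biases the result toward benefit: the documents show missing scores, not their values, and Section 13 specifies no analysis, so reliance on on-treatment scores is inferred from the schedule. The other is that the year-2 timing prevents comparison with final hearing and imaging: the course-24 date is itself inferred, the offset is 8 weeks at one visit, and six earlier visits align. The primary conclusions, sample size, alpha and power are unaffected. This should be corrected, but it does not threaten the trial.

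**What to change.** In the Section 10 calendar, mark the NFTI-QOL row under completion/discontinuation of treatment. The same mark gives patients who complete treatment a score at the end of course 26, alongside the final MRI and hearing test, so course 24 need not be dropped.

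In Section 13, state that the score at discontinuation will be reported together with the by-course summary, with the number of patients contributing at each point. A single baseline-to-last-score analysis is not needed: it would mix follow-up times from weeks to two years.

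The cost is an 8-item form taking a few minutes at an existing visit, and possibly a less favorable quality-of-life result.

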11 MEASUREMENT OF EFFECT

11.1 Hearing Response Criteria (Stratum 1 only)

Hearing is monitored in clinical practice by measuring pure tone thresholds, word recognition scores, brainstem auditory evoked responses (BAERs), and otoacoustic emissions (OAEs).

Pure tone thresholds measure the minimum sound level that an ear can perceive. Thresholds are typically measured at octaves and half-octaves from 250 Hz to 8000 Hz. An average of thresholds at 500, 1000, 2000 and 4000 Hz (PTA) is recommended as a standard outcome measure by the American Academy of Otolaryngology, Head and Neck Surgery (AAO-HNS) for reporting in cases of VS.

Word recognition scores measure the ability to recognize (as opposed to detect) auditory information. Patients are presented a list of 50 words at a fully audible level and the percentage identified correctly is the score. This study will use full 50-item monosyllable lists and standardized recordings.

Because tumors associated with NF2 have benign histology, overall survival is not an appropriate endpoint for clinical trials in this condition. Instead, the goal of treatment is to minimize neurologic morbidity (including hearing loss) and to defer surgical treatments that may cause iatrogenic dysfunction. For this reason, hearing function is the most important way to monitor the activity of new agents designed to treat VSs.

Word recognition is the measure most closely associated with daily hearing function since it measures the ability to comprehend speech. If word recognition quality improves, the patient can converse successfully, even if a hearing aid is needed to make sounds sufficiently loud. Statistical methods have been developed to determine significant changes in this measure. Word recognition scores represent summary scores from a collection of binary endpoints (correct/incorrect responses) and thus follow a binomial distribution (e.g., non-Gaussian

^{**} Please note that Grade 3 asymptomatic elevations of CPK do not require a dose reduction

distribution). Although it is tempting to use a set change in word recognition score (e.g., fifteen percentage points) as a clinical response, this approach is inappropriate given the binomial model of variance. A more rigorous approach involves the use of the 95% (p=0.05) critical difference table⁴⁴. The 95% critical differences for 50-word lists as proposed here have been used in previous studies⁴⁵ and in clinical trials evaluating the effect of drug treatment on hearing.

- 11.1.1 Hearing Response (HR): Improvement in word recognition score above the 95% critical difference, taking as reference the baseline word recognition score (APPENDIX E)
- 11.1.2 Stable Hearing (SH): Persistence of word recognition score within the 95% critical difference, taking as reference the baseline word recognition score (APPENDIX E)
- 11.1.3 Progressive Hearing Loss (PHL): Decline in word recognition score below the 95% critical difference, taking as reference the baseline word recognition score (APPENDIX E)

Duration of hearing response: The duration of hearing response (HR) is measured from the time that measurement criteria are met for HR until the first date that the word recognition score decreases beneath the upper limit of the 95% critical difference of the baseline word recognition score.

Duration of stable hearing: Stable disease is measured from the start of the treatment until the criteria for progression are met, taking as reference the word recognition score recorded at baseline

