3 PATIENT SELECTION

3.1 Inclusion Criteria:

3.1.1 Patients must have a confirmed diagnosis of neurofibromatosis 2 by fulfilling National Institute of Health (NIH) criteria or Manchester criteria, or by detection of a causative mutation in the NF2 gene.

The NIH criteria includes presence of:

- Bilateral vestibular schwannomas, OR
- First-degree relative with NF2 and **EITHER** unilateral eighth nerve mass **OR** two of the following: neurofibroma, meningioma, glioma, schwannoma, juvenile posterior subcapsular lenticular opacity.

The Manchester criteria includes presence of:

- Bilateral vestibular schwannomas, **OR**
- First-degree relative with NF2 and **EITHER** unilateral eighth nerve mass **OR** two of the following: neurofibroma, meningioma, glioma, schwannoma, juvenile posterior subcapsular lenticular opacity, **OR**
- Unilateral vestibular schwannoma **AND** any two of: neurofibroma, meningioma, glioma, schwannoma, juvenile posterior subcapsular lenticular opacity, **OR**
- Multiple meningiomas (two or more) **AND** unilateral vestibular schwannoma **OR** any two of: schwannoma, glioma, neurofibroma, cataract.
- 3.1.2 Patients do not need to have a histologic diagnosis in order to start therapy but must have measurable disease (in 2 dimensions) on MRI scan to be eligible.

3.1.2.1 For Stratum 1: Patients must have a target VS with the following qualities:

Associated with a word recognition score of < 85% and > 0%

AND

Documented progression defined as: Either progressive hearing loss or progressive tumor growth in last 18 months defined as $\geq 20\%$ increase in volume.

3.1.2.2. For Stratum 2: Patients must not meet the eligibility criteria as stated for Stratum 1 and have a target lesion that has exhibited progression. Progression is defined as: $\geq 25\%$ increase in sum of the products of perpendicular diameters of lesions in the preceding 18 months; any new lesion; or clinical deterioration related to disease.

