APPENDIX E Hearing Response Guidelines:

Clinical criteria for definition of hearing response based on a 50-word hearing test. Upper and lower limits for the 95% critical differences for percentage scores are adapted from Thornton. REF

Baseline word recognition score (%)	cognition difference (%) Re		Progressive hearing loss (%)
0	0–4	≥ 6	n/a
2	0-10	≥ 12	n/a
2 4	0-14	≥ 16	n/a
6	2–18	≥ 20	0
8	2–22	≥ 24	0
10	2–24	≥ 26	0
12	4–26	≥ 28	≤ 2
14	4–30	≥ 32	= 2 ≤ 2
16	6–32	≥ 34	-
18	6–34	≥ 36	≤ 4
20	8–36	≥ 38	≤ 6
22	8–40	≥ 42	≤ 6
24	10–42	≥ 44	-
26	12–44	≥ 46	≤ 10
28	14-46	≥ 48	≤ 12
30	14–48	≥ 50	≤ 12
32	16–50	≥ 52	- 12 ≤ 14
34	18–52	≥ 54	≤ 16
36	20–54	≥ 56	≤ 18
38	22–56	≥ 58	≤ 20
40	22-58	≥ 60	≤ 20
42	24–60	≥ 62	≤ 22
44	26–62	≥ 64	− ≤ 24
46	28-64	≥ 66	≤ 26
48	30–66	≥ 68	≤ 28
50	32–68	≥ 70	≤ 30
52	34–70	≥ 72	≤ 32
54	36–72	≥ 74	≤ 34
56	38-74	≥ 76	≤36
58	40–76	≥78	≤38
60	42-78	≥ 80	≤ 40
62	44–78	≥ 80	≤ 42
64	46–80	≥ 82	≤ 44
66	48-82	≥ 84	≤ 46
68	50-84	≥ 86	≤ 48
70	52-86	≥ 88	≤ 50
72	54–86	≥ 88	≤ 52

Baseline word recognition score (%)	95% critical difference (%)	Hearing Response (%)	Progressive hearing loss (%)
74	56–88	≥ 90	≤ 54
76	58–90	≥ 92	≤ 56
78	60–92	≥ 94	≤ 58
80	64–92	≥ 94	≤ 62
82	66–94	≥ 96	≤ 64
84	68–94	≥ 96	≤ 66
86	70–96	≥ 98	≤ 68
88	74–96	≥ 98	≤ 72
90	76–98	100	≤ 74
92	78–98	100	≤ 76
94	82–98	100	≤ 80
96	86–100	n/a	≤ 84
98	90–100	n/a	≤ 88
100	96–100	n/a	≤ 94

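### The end rule for duration of hearing response misses by one score: a result exactly at the upper critical limit is stable hearing but does not end the response

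*Combined protocol and SAP*

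**What the plan says.** Section 11.1 of the combined protocol and SAP classifies word recognition against a critical range around the baseline score. Response (11.1.1) is "Improvement in word recognition score above the 95% critical difference". Stable hearing (11.1.2) is "Persistence of word recognition score within the 95% critical difference". Both definitions refer to Appendix E, which lists for each baseline the critical range, the response threshold and the progressive-loss threshold. The appendix introduces the range by its two ends: "Upper and lower limits for the 95% critical differences for percentage scores are adapted from" a published table.

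The duration paragraph at the end of the hearing criteria starts the clock when the response criterion is met and stops it at "the first date that the word recognition score decreases beneath the upper limit of the 95% critical difference" of the baseline score.

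Three other provisions set the scale:

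- Scoring (11.1): "Patients are presented a list of 50 words at a fully audible level and the percentage identified correctly is the score".
- Entry to stratum 1 (3.1.2.1): the target tumor must be "Associated with a word recognition score of < 85% and > 0" percent.
- Timing (Section 10, footnote C): hearing is tested before therapy and after courses 3, 6, 9, 12, 16, 20 and 26. The Schema sets a course at 28 days.

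**The concern.** The start and end rules do not meet. A response starts only above the critical range, so it should end once the score is back inside that range, and the upper limit is inside it. The end rule instead waits for a score below the limit. A visit exactly at the limit is therefore stable hearing by category and continuing response by duration.

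Two analysts applying different paragraphs of 11.1 to the same data could report different end dates. The discrepancy runs in one direction, toward longer responses. Because tests are 12 to 24 weeks apart, a difference of one word can move an end date by months.

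**Working it through.** The plan gives no numerical figure for duration of response, so there is none to reproduce. The check compares the rules with Appendix E and then asks how often the affected score would occur.

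**1. Attainable scores.** With 50 words, scores move in steps of 100/50 = 2 points. Entry above 0% and below 85% allows baselines 2, 4, …, 84, which is 42 rows of Appendix E.

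**2. Threshold against limit.** Let U be the upper limit of the critical range and H the response threshold. In all 42 rows H = U + 2. For example:

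| Baseline | Range | U | H | Score = U: category | Score = U: ends duration? |
|---|---|---|---|---|---|
| 40 | 22–58 | 58 | 60 | stable hearing | no, 58 is not below 58 |
| 50 | 32–68 | 68 | 70 | stable hearing | no, 68 is not below 68 |
| 84 | 68–94 | 94 | 96 | stable hearing | no, 94 is not below 94 |

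H is the next attainable score above U, so U is the only score in conflict. One step lower (56 at baseline 40) ends the response under the current text.

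**3. Strict or loose wording.** For progressive hearing loss, 11.1.3 speaks of a decline below the range. At baseline 40 Appendix E puts this at 20 or less, one step under the lower limit of 22. There the limit itself is excluded from the worse category. Reading the duration rule the same way excludes U from ending the response. No other section settles the matter.

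**4. Time added per occurrence.** The gaps between tests are 3 × 4 = 12 weeks through course 12, 4 × 4 = 16 weeks from course 12 to course 20, and 6 × 4 = 24 weeks from course 20 to course 26. A visit at U moves the recorded end to a later test, so by at least one such gap. If it is the last test, the response is censored instead of ended.

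**5. How often a visit lands on U.** Section 11.1 treats the score as binomial. For a true score of t percent,

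P(score = U) = C(50, k) (t/100)^k (1 − t/100)^(50 − k), with k = U/2.

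The documents give no on-treatment distribution, so t is an assumption and is varied here:

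| True score t | Baseline 40 (U = 58, k = 29) | Range over 42 baselines |
|---|---|---|
| U | 11.4% | 11–23% |
| U + 2 (the response threshold H) | 10.9% | 11–18% |
| U + 4 | 9.6% | 6–13% |
| U + 10 (capped at 99%) | 3.8% | 0.01% to about 4% |

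With the true score at H, 24% to 57% of the tests that fail the response criterion fall exactly on U, depending on baseline. Those tests would not end the duration.

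**6. What does not move.** The stratum 1 decision counts responses at 24 weeks using 11.1.1, not the duration rule. The Simon figures in 13.2 reproduce: the stopping probability at a true rate of 0.05 is 0.95^9 = 0.630 (stated 0.63), and the power at 0.25 is 0.812 (stated 0.81). Neither uses duration.

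**The case against.** The strongest reply is that this is loose wording rather than a second threshold. Appendix E assigns every attainable score to one category, and an analyst would probably end the response when the table stops calling it one. That makes actual misdating less likely. It does not reconcile the text, because someone who applies the sentence literally gets a different date.

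The second reply is that little depends on it. Duration of hearing response is not among the objectives in Section 1, Section 13 plans no analysis of it, and the end date is not tied to any treatment decision. Stratum 1 has at most 17 subjects. At the design rate of 0.25 that means about 17 × 0.25 = 4 responders, so perhaps one or two dates in a descriptive summary could change. This stands and limits the importance of the point.

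The third reply concerns the percentages. The 11–23% figure supposes a responder whose true score is at the limit, which the table itself calls stable hearing. For a clear improvement the chance is small, at most about 4% at 10 points above the limit. This also stands, and it is why the full range is shown.

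A reader might infer that stable-hearing visits in general are counted as response time, or that the efficacy result is inflated. The documents support neither: any score below the limit ends the response, and the primary endpoint is classified by 11.1.1 and Appendix E without reference to duration.

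**Conclusion.** The inconsistency is real and narrow. Read literally, the duration rule keeps a response running at one score that 11.1.2 and Appendix E call stable hearing. It affects one score at each of the 42 eligible baselines and can only lengthen durations, by at least 12, 16 or 24 weeks where a later test exists, or by censoring a response that had ended.

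The conflict itself rests only on the text and the table. Its frequency rests on an assumed true score and the binomial model: 11–23% per visit for a patient at the limit, falling to about 4% or less for one 10 points above it. It therefore concerns borderline responders. This is a minor wording error in a descriptive measure, worth correcting because the correction is cheap.

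**What to change.** Replace the end rule in the duration paragraph of 11.1 with: until the first date on which the word recognition score no longer meets the Hearing Response column of Appendix E for that baseline, that is, the score is at or below the upper limit of the critical range.

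At baseline 40% the duration would then end at 58 or less instead of 56 or less. The cost is one sentence and no new data, and reported durations become slightly shorter. The response definition, the 24-week endpoint, the sample size and the decision rule stay as they are.
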